8.3 Primary Analysis

The primary analysis will characterize the concordance of clinically relevant *EGFR* alterations (see appendix I) detected in plasma versus tumor tissue for patients with stage IV non squamous NSCLC. PPA, NPA and overall concordance will be calculated across all *EGFR* alterations, for all sensitizing alterations and for each individual alteration, separately.

Two tables (Tables 4A and 4B) will be constructed and PPA, NPA, overall agreement and corresponding confidence intervals will be calculated as shown below. Of note, the NPA will be calculated based only on patients enrolled regardless of presence or absence of the genomic alterations (Section 4, Table 2). Patients enrolled after this initial period due to presence of *ALK* alteration in tissue will not be included in this analysis as they are unlikely to have *EGFR* mutations and their inclusion could result in overestimation of NPA.

Table 4. Calculation of PPA and NPA.

4A: Table based on all patients with available tissue biopsy with *EGFR* alterations detected in tumor tissue

Genomic Health liquid biopsy mutation panel	EGFR alteration detected in tumor tissue
EGFR alteration detected	a
EGFR alteration not detected	c
Total	a+c

$$\text{Positive Percent Agreement (PPA)} = a / (a+c) * 100\%$$

CONFIDENTIAL – PROPRIETARY PROPERTY OF GENOMIC HEALTH, INC.

Study Protocol

4B. Table based on all patients with available tissue biopsy enrolled regardless of presence or absence of genomic alterations as described in Section 4 and Table 2.

Genomic Health liquid biopsy mutation panel	EGFR alteration not detected in tumor tissue
EGFR alteration detected	b
EGFR alteration not detected	d
Total	b+d

Negative Percent Agreement (NPA) = $d / (b+d) * 100\%$

If all patients were enrolled regardless of alteration status, the overall agreement would be calculated as $(a+d)/(a+b+c+d) * 100\%$. However, since some patients are enrolled based on known alteration status, the overall agreement will be calculated as a weighted proportion to account for enrichment of the number of patients with marker positive tumors. Details of the calculations will be provided in the Statistical Analysis Plan.

8.4 Secondary Analyses

Secondary analyses will include assessments of PPA, NPA and overall agreement calculated as described in section 8.3 for *ALK* alterations (objective 6.2.1) and all other detected alterations (objective 6.2.2).

In addition, we will report:

- 1) the total number of all alterations detected in plasma, tumor tissue, or both.
- 2) the number of patients with at least one alteration with clinical relevance detected in plasma, tumor tissue, or both.
- 3) the number of hotspot mutations and non-hotspot mutations detected in plasma, tumor tissue, or both.

The results will be presented separately for single nucleotide variant (SNV), copy number variant (CNV) and structural variant (indels, insertions, translocations) alterations.

As described in study objective 6.2.3, mutation-specific NCCN-guideline based clinical actions based on alteration status in plasma will be compared to those based on tissue

CONFIDENTIAL – PROPRIETARY PROPERTY OF GENOMIC HEALTH, INC.

Study Protocol

and the actual treatment received based on findings in tumor tissue. For each patient, a clinical action will be defined in agreement with NCCN guidelines based on detected key genomic alterations and prior targeted therapies to mimic the clinical context for decision making. A detailed description of each clinical action will be provided in the Statistical Analysis Plan. To assess concordance of clinical actions based on alterations identified in plasma vs those based on tissue as well as concordance of clinical actions based on alterations identified in plasma and the actual treatment received based on tumor tissue findings, PPA, NPA and overall agreement will be calculated.

We will assess PPA, NPA and overall agreement separately for patients with newly diagnosed metastatic disease and patients who progressed on treatment (study objective 6.2.4).

The concordance analyses will also be conducted in the subset of patients with available central CLIA laboratory assessment of tumor tissue.

In addition, we will summarize the distribution of all genomic alterations detected in plasma, tumor tissue, or both using tabulations, histograms and descriptive statistics (study objective 6.2.5). We will provide such summaries for individual alterations, sensitizing vs resistance alterations within a gene (if applicable), all alterations within a given gene and across all genes.

The detection of *EGFR* T790M alterations in plasma samples will be characterized descriptively in patients progressing on EGFR targeted therapy (erlotinib, gefitinib, afatinib) (study objective 6.2.6).

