6.2 Secondary Objectives

6.2.1 Assess concordance of genomic alterations in *ALK* (EML4-ALK fusions) detected in plasma versus tumor tissue.

6.2.2 Assess concordance of all detected alterations in plasma versus tumor tissue.

CONFIDENTIAL – PROPRIETARY PROPERTY OF GENOMIC HEALTH, INC.

Study Protocol

- 6.2.3 Assess concordance of mutation-specific NCCN guideline-based clinical actions based on alterations found in plasma versus tumor tissue and versus treatment received based on findings in tumor tissue.
 - 6.2.4 Assess concordance of detected genomic alterations separately in patients with newly diagnosed metastatic disease and patients progressing on treatment.
 - 6.2.5 Summarize the distribution of genomic alterations present in plasma, tumor tissue or both overall.
 - 6.2.6 Characterize the detection of *EGFR* T790M alterations in plasma in patients progressing on EGFR targeted therapy (erlotinib, gefitinib, afatinib).
- 6.3 Exploratory Objectives
- 6.3.1 Explore the association of genomic alterations detected in plasma or tumor tissue and time to progression, defined as first objective sign of progression by clinical examination or imaging, and response to therapy initiated after the liquid biopsy test.
- 6.4 Measures to Minimize Bias

Genomic Health staff involved in the processing of liquid biopsy samples will remain blinded to the central assessment of FPE tissue, Pathology and Clinical data collected during the study. The Genomic Health staff involved in the central assessment of FPE tissue will be blinded to the results of the liquid biopsy.

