8. STATISTICAL METHODS

8.1 General Methods

This section provides a general description of the statistical analysis methods. A detailed description of the analysis methods will be provided in the Statistical Analysis Plan, that will be developed blinded to any analytical test results (i.e. from the liquid biopsy tests and tumor tissue assessments) and finalized prior to the data lock for the interim analysis.

This is a descriptive study to characterize the concordance between the results of the Genomic Health LBMP based on plasma and genomic assessment of the tumor tissue. Both the liquid biopsy and the tumor tissue assessments will report the status of the investigated alterations in a binary manner as detected or not detected. No formal hypothesis testing is planned. Unless otherwise stated, two-sided 95% Clopper-Pearson confidence intervals will be reported²⁸.

The analysis of a single tumor biopsy cannot yield a reference standard for a liquid biopsy assessment due to tumor multifocality and intra- and inter-tumor heterogeneity in stage IV disease. As described in the FDA Statistical Guidance on Reporting Results from Studies Evaluating Diagnostic Tests (2007), when a new test is evaluated by comparison to a non-reference standard, it is not possible to directly calculate unbiased estimates of sensitivity and specificity. Therefore, due to lack of reference standard for analysis of liquid biopsies, it would not be appropriate to describe the comparative results of the study in terms of sensitivity and specificity. Instead, we will characterize the concordance in terms of positive percent agreement (PPA) and negative percent agreement (NPA) as presented in section 8.3, Table 4.

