8.2 Analysis Populations

Statistical analyses will involve samples from patients with stage IV non squamous NSCLC. Samples that are not collected according to the sample preparation instructions, fail pathology review, fail to meet pre-specified analytical quality control metrics as defined by the Genomic Health LBMP's standard operating procedures, or fail to meet pre-specified quality control specification for the FPE assessment will be considered non-evaluable and will not be included in the analyses described in this section. Approximately 20% of enrolled patients are expected to have non-evaluable samples and thus results from approximately 248 evaluable patients are expected to be included in the analyses.

CONFIDENTIAL – PROPRIETARY PROPERTY OF GENOMIC HEALTH, INC.

Study Protocol

The primary analysis will be based on patients with non squamous NSCLC with evaluable plasma and tissue samples and reportable results from both the Genomic Health liquid biopsy test and tumor tissue assessments. The results of the central tissue assessments will be used when available. In patients without central CLIA laboratory results, local assessments of genomic alterations in tissue will be utilized. Exploratory analyses will include patients with evaluable samples from the Genomic Health liquid biopsy test and time to progression and available assessment of best response to therapy initiated after the liquid biopsy test.

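### Do the plasma/tissue/both counts in Section 8.4 need a rule for alterations that the tissue test did not cover?

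*Combined protocol and SAP*

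**What the plan says.** Section 8.4 lists three descriptive counts. The first is "the total number of all alterations detected in plasma, tumor tissue, or both", the second is "the number of patients with at least one alteration with clinical relevance detected in plasma, tumor tissue, or both", and the third splits hotspot from non-hotspot mutations in the same way. For objective 6.2.5 ("Summarize the distribution of genomic alterations present in plasma, tumor tissue or both overall") it adds summaries by individual alteration and for "all alterations within a given gene and across all genes". It also states: "The concordance analyses will also be conducted in the subset of patients with available central CLIA laboratory assessment of tumor tissue".

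Section 8.1 says that the plasma and tissue assessments "will report the status of the investigated alterations in a binary manner as detected or not detected", that no hypothesis test is planned, and that detailed methods go into a separate SAP, written blinded and finalized before the interim data lock. That SAP is not part of the document under review.

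Section 8.2 first removes non-evaluable samples from every analysis in Section 8. It then bases the primary analysis on patients with "reportable results from both the Genomic Health liquid biopsy test and tumor tissue assessments", and says that "Exploratory analyses will include patients with evaluable samples from the Genomic Health liquid biopsy test" together with outcome data. It has no sentence for the secondary analyses. It uses central tissue results where they exist and local results otherwise.

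**The concern.** The two tests need not cover the same ground. Table 1 lists 17 genes for the plasma panel. Tissue is tested by local standard of care at about 25 sites, with no minimum coverage stated, and the share of patients with a central result is not given. Section 2 links only EGFR and ALK to agents approved in NSCLC, which leaves 15 panel genes whose tissue coverage is unknown.

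If a plasma finding in an unassayed gene is filed as plasma-only, that group mixes two situations: tissue tested and negative, and tissue never tested. A reader could take a large plasma-only group as evidence that plasma sees what a single biopsy misses, an advantage that Section 2 offers for the test. Part of it would then reflect local test menus.

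The sharpest example is EGFR T790M in patients progressing on EGFR-targeted therapy. For them concurrent tissue is not mandatory, and under Appendix II the mutation report may come from the primary tumor.

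**Working it through.** **The plan's own figures.** Sections 8.2 and 8.7 assume about 20% losses.

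- All patients: 310 × 0.80 = 248, as stated in Section 8.2.
- Plasma and tissue: 260 × 0.80 = 208, as stated in Section 8.7 for the concordance analyses.
- Plasma only: 50 × 0.80 = 40, as stated in Section 8.7 for T790M.
- 208 + 40 = 248.

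The 248 therefore contain 40/248 = 16.1% for whom concurrent tissue is not mandatory. At the 50% T790M rate in Section 8.7, about 40 × 0.50 = 20 of them carry T790M. These figures also show that Section 8.7 gives an expected number for concordance and another for T790M (objective 6.2.6), although Section 8.2 has no secondary heading.

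**Effect on the counts under the literal reading.** Let u be the share of plasma-detected alterations not covered by that patient's tissue test, and d the plasma-only share where tissue was tested. Both are assumptions. Reported plasma-only share = u + (1 − u)d.

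| d | u = 10% | u = 25% | u = 50% |
|---|---|---|---|
| 5% | 14.5% | 28.8% | 52.5% |
| 10% | 19% | 32.5% | 55% |
| 20% | 28% | 40% | 60% |

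For example, 0.25 + 0.75 × 0.10 = 0.325. At u = 0 there is no effect. The formula shows what the literal reading would do. It does not show that the reading will be used, or how large u is.

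**Effect on NPA if untested were coded negative.** Assume 200 × 0.80 = 160 evaluable First Phase patients, plasma detection of 80% and NPA of 99% where tissue was tested. At the protocol's 5% ALK prevalence, and now with u as the share of patients not tested in tissue:

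- u = 10%: 1 − 2.16/152.8 = 98.6%.
- u = 50%: 1 − 4.72/156 = 97.0%.

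Both lie inside the 95% Clopper-Pearson interval for 150/152, which is 95.3% to 99.8%. For a more common alteration the shift would be larger. At an assumed 25% prevalence with 20% of patients untested, NPA would read 94.1%. Such coding would be a real error, so the question is whether the plan calls for it.

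**Does the plan call for it?** Set the provisions side by side.

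1. To place a finding under plasma and not under both, the analyst must know its tissue status. Section 8.1 gives a status only to alterations that were investigated. An unassayed gene has none. This reading excludes untested alterations from PPA and NPA, and it applies equally to the counts in the same section.
2. Table 4B in Section 8.3, whose method Section 8.4 adopts, asks only for an available tissue biopsy. Its row and column labels still need a detected or not-detected result, so it does not direct that untested means negative.
3. Sections 4, 4.1 and 7.5 say that local results are used. Section 8.2 sets the order, central first and local as fallback, and the synopsis repeats it. The comparator is therefore settled for analysis.
4. Mutation reports are required at enrollment (Table 3 and Appendix II), and Section 7.5 has measures from them entered in the data capture system. Where a report states what was tested, coverage can be recovered.

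**The case for a change.** The best case for a change is that the wording really is silent. Section 8.4 speaks of all alterations and all genes, has no not-tested class, and sits beside an analysis-sets section that omits the secondary analyses. The evaluability rule in Section 8.2 concerns sample collection, pathology and quality control, not gene coverage. The central-laboratory subset repeats the concordance analyses, not clearly the counts, and leaves out locally tested patients. The repair would be a few sentences, and coverage is easier to record before data lock than after.

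Most of that stands as description. Nothing in the protocol classes a T790M finding in a patient without concurrent tissue, and the gap is not confined to secondary genes, because the counts include T790M and EGFR copy-number gains.

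It does not show an error. Section 8.4 promises numbers and tabulations of where alterations were found, and an alteration found in plasma was found there whether or not tissue was tested. No section defines a plasma-only share or ties these counts to a claim that plasma outperforms biopsy; the remark on heterogeneity in Section 2 is background. The summaries by gene and by alteration let a reader separate well-covered genes from the rest. How to code an unassayed gene is ordinary SAP content, and Section 8.1 says that the SAP will hold such detail.

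**Conclusion.** No change to the plan is needed. This is missing detail that an analyst would fill sensibly: compare plasma with tissue only for alterations assayed in both, and list plasma findings without a tissue test separately. Saying so in the SAP, for the counts and the secondary PPA and NPA, would be a courtesy to the reader.

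The size of any effect cannot be derived from the documents. The table above depends wholly on assumed values of u and d. The figures of about 40 patients and about 20 T790M carriers do come from the plan, but they become misclassified only if someone treats absent tissue as negative tissue, which the plan does not direct.

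The conclusion rests on reading Section 8.1 the same way for counts as for agreement rates, and on the SAP being finalized blinded as promised. The primary EGFR analysis requires reportable results from both tests and is not in question. Sample size and planned intervals do not move.

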4.1 Required Procedures at Clinical Sites

Participants who are eligible and consent to participate in the study will provide a venous blood sample (2X 10 mL Streck tubes) at a single study related visit. Participants will have no further visits as part of this study. Participants data will be collected at time of progression or at 12 months after blood sample collection, whichever occurs first and in addition, data will be collected to permit outcome analysis of the interim analysis. Participation in the study will not alter clinical care. All other clinical procedures performed and collection of non-study data will be in accordance with each participating institution’s standard of care. Local assessment of tumor tissue samples will be performed at each participating institution as per their clinical standard of care practices and results from the local assessment of genomic alteration status will be used. Each site will need to provide a single H&E slide to Genomic Health for an independent pathology review.

CONFIDENTIAL – PROPRIETARY PROPERTY OF GENOMIC HEALTH, INC.

	<h2>Study Protocol</h2>
---	-------------------------

Table 3. Requirements by patient category to help identify correct patients and required materials at the single required patient visit. Detailed overview in Table 6 (page 39).

Requirements	Patient Category (see Figure 1)		
	A: Newly diagnosed with stage IV disease	A: Patient progressing on treatment (except if progressing on erlotinib, gefitinib, or afatinib)	B: Patient progressing on erlotinib, gefitinib, or afatinib
Biopsy/cytology/excision performed on primary or metastatic lesion	X		
Biopsy/cytology/excision performed on metastatic lesion		X	Only if available
Local pathology report	X	X	X (original diagnosis)
Local mutation report	X	X	X (original diagnosis)
Provide H&E slide from biopsy/cytology/excision to Genomic Health for independent review	X	X	X
Blood sample (2X 10 mL) collected in Streck tubes	X Prior to initiating new systemic anti-tumor treatment AND no more than 8 weeks after tissue biopsy	X Prior to initiating new systemic anti-tumor treatment AND no more than 8 weeks after tissue biopsy	X Prior to initiating new systemic anti-tumor treatment AND no more than 8 weeks after tissue biopsy only in cases where a biopsy was performed

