5.1 Inclusion Criteria

- 5.1.1 Subjects must be 18 years or older.
- 5.1.2 Patients with stage IV non squamous NSCLC who are either newly diagnosed or progressing on any treatment (progression defined as increasing tumor size or new metastatic lesions on clinical or imaging assessment).
- 5.1.3 Patients with available tissue sample from a metastatic site or, if the patient presents with stage IV disease at diagnosis, from the primary tumor or a metastatic site. If a patient is progressing on EGFR targeted therapy (erlotinib, gefitinib, afatinib), tumor tissue sample is required only if available.
- 5.1.4 No new systemic anti-tumor therapy administered in the interval between the tissue biopsy and collection of the blood sample. (interval not to exceed eight weeks). Local radiation therapy is permitted.
- 5.1.5 Able and willing to read, understand and sign an informed consent and Health Insurance Portability and Accountability Act (HIPAA) authorization, or equivalent privacy law, where this is applicable.

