5.2 Exclusion Criteria

- 5.2.1 Patients who are currently receiving therapy (targeted, immune- or chemotherapy) without sign of progression.
- 5.2.2 Patients with squamous NSCLC.
- 5.2.3 Patients with more than 8 weeks between collection of tumor specimen and collection of blood sample for analysis. (Not applicable for patients progressing on EGFR targeted therapy with no biopsy at progression)

CONFIDENTIAL – PROPRIETARY PROPERTY OF GENOMIC HEALTH, INC.

Study Protocol

- 5.2.4 Patients changing EGFR therapy due to toxicity or preference without documented disease progression.
 - 5.2.5 Patients progressing on Osimertinib treatment.
 - 5.2.6 Patients with brain metastases only.
 - 5.2.7 Inability to comply with study and/or follow-up procedures.
 - 5.2.8 Unable or unwilling to provide written informed consent.
- 5.3 Study Duration and Withdrawal

Study participation for subjects ends after the research blood sample is drawn. There is no study-related follow-up with the participants but time to progression on therapy given after liquid biopsy or disease status at one year after liquid biopsy will be captured.

Subject participation is voluntary and can be discontinued at any time without loss of benefits or penalty. Should this occur, the reason for withdrawal must be documented in the original source document for the subject and written notification provided to Genomic Health. Participants are notified through the informed consent process that any de-identified research blood and tissue samples will be destroyed upon their request and not used for further analysis. If requested by the Investigator, a participant may be asked to discontinue the study if they are unable to meet the protocol defined study requirements.

Subjects that are screened but who are unable to undergo a successful blood draw or do not meet the protocol requirements will be considered screen failures.

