6. STUDY OBJECTIVES

6.1 Primary Objective

Assess concordance of genomic alterations in *EGFR* (see appendix I) detected in plasma versus tumor tissue in stage IV non squamous NSCLC patients who are newly diagnosed or progressing on treatment.

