APPENDIX II

Table 6. Requirements for patients included in category A (See Figure 1)

Patient category:	Enrollment visit requirements	Follow up requirements

Newly diagnosed stage IV patient:
 
 1. Patients regardless of genomic alteration status in tumor (During First Enrollment Phase only) 2. EGFR alterations in tumor 3. ALK alterations in tumor 	
 -Available tumor tissue sample from primary or metastatic lesion. -Pathology report -Mutation report -Clinical data entry in EDC 	
 -Date of progression on first therapy initiated after liquid biopsy, one year after liquid biopsy if still responding, or date of patient death should that occur prior to first progression or 1 year after liquid biopsy. -Clinical and selected treatment data entry in EDC

Patient progressing on therapy (except if progressing on EGFR inhibitors- see below):
 
 1. Patients regardless of genomic alteration status in tumor (During First Enrollment Phase only) 2. EGFR alterations in tumor 3. ALK alterations in tumor 	
 -Available tumor tissue sample from metastatic lesion. -Pathology report -Mutation report -Clinical data entry in EDC 	
 -Date of progression on first therapy initiated after liquid biopsy, one year after liquid biopsy if still responding, or date of patient death should that occur prior to first progression or 1 year after liquid biopsy. -Clinical and selected treatment data entry in EDC

CONFIDENTIAL – PROPRIETARY PROPERTY OF GENOMIC HEALTH, INC.

	<h2>Study Protocol</h2>
---	-------------------------

Requirements for patients included in category B (See Figure 1)

Patient category:	Enrollment visit: requirements	Follow up requirements

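### Does the plasma-only label in section 8.7 keep patients progressing on EGFR inhibitors out of the EGFR agreement analysis?

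*Combined protocol and SAP*

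**What the plan says.** Section 6.1 sets the primary objective as EGFR concordance "in stage IV non squamous NSCLC patients who are newly diagnosed or progressing on treatment". Objective 6.2.4 and section 8.4 then promise the agreement measures separately for the two groups: "We will assess PPA, NPA and overall agreement separately for patients with newly diagnosed metastatic disease and patients who progressed on treatment".

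The patient categories in Table 3 and Appendix II (Table 6) split the progressing patients. Category A takes "A: Patient progressing on treatment (except if progressing on erlotinib, gefitinib, or afatinib"; Table 6 puts it as "Patient progressing on therapy (except if progressing on EGFR inhibitors- see below". Patients progressing on the three named drugs form category B. Section 5.2.5 excludes "Patients progressing on Osimertinib treatment" from the study altogether.

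For category B, section 5.1.3 says that a "tumor tissue sample is required only if available", and Table 3 sets the blood draw at "no more than 8 weeks after tissue biopsy only in cases where a biopsy was performed". Table 6 calls tissue at progression preferable.

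Section 8.7 plans 208 evaluable patients for concordance out of 260, and 40 evaluable out of 50 for T790M detection. Where it first gives these numbers it describes the 50 as having plasma and nothing else. The paragraph after Table 5 repeats that label but adds in parentheses that tissue is not compulsory for them.

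The analysis rules are in 8.2 and 8.3. Section 8.2 bases the primary analysis on patients with usable plasma and tissue and a reportable result from each. The heading of Table 4A, which gives the PPA, reads "Table based on all patients with available tissue biopsy with *EGFR* alterations detected in tumor tissue".

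**The concern.** Taken with Tables 3 and 6, the first description in 8.7 seems to close off one promised result. If every patient progressing on an EGFR inhibitor is plasma-only, the EGFR-positive progressing pairs must all come from patients progressing on something else. Section 2 names the same three drugs as the approved agents for sensitizing EGFR mutations, so that group could be small, and the plan gives no number for it. The primary PPA would then be close to a PPA for newly diagnosed patients, and the 6.2.4 result for progressing patients might rest on a handful.

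There is also an apparent conflict. The heading of Table 4A would admit a category B patient with an EGFR-positive progression biopsy, whereas the allocation in 8.7 does not count one. If two analysts could build different denominators for the primary PPA, that would matter.

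**Working it through.** **1. The plan's own figures.** Inputs from 8.7 and Table 2: 260 patients with tissue and plasma, 50 in the T790M group, 69 EGFR-positive, 20% losses, and two-sided 95% Clopper-Pearson intervals (8.1).

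- 260 × 0.8 = 208; 50 × 0.8 = 40; 310 × 0.8 = 248. All match.
- EGFR-positive and evaluable: 69 × 0.8 = 55.2. At 45% prevalence for each of the two main alterations, 55.2 × 0.45 = 24.8 (plan: about 25 each) and 55.2 × 0.9 = 49.7 (plan: 50).
- Clopper-Pearson lower limit = Beta quantile at 0.025 with parameters (x, n − x + 1); upper limit = Beta quantile at 0.975 with (x + 1, n − x). For 40/50 this gives 0.663 to 0.900; the plan states a lower bound of 0.66.

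No stated figure is wrong.

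**2. Which text decides who is analysed.**

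| Place | Function | Category B patient with a progression biopsy |
|---|---|---|
| 8.2 | Defines the primary analysis population | In: requires usable plasma and tissue, no limit by category |
| 8.3, Table 4A | Defines the PPA denominator | In: any patient with available tissue and a tissue EGFR alteration |
| 5.1.4, 5.2.3, Table 3 | Interval and no-new-therapy rules | Apply whenever a biopsy was done |
| 8.7, first mention | Plans numbers | Not counted |
| 8.7, after Table 5 | Plans T790M precision | Tissue described as optional |

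Where 8.3 wants an exclusion it states one: patients enrolled later because of an ALK alteration are kept out of the NPA, with a reason. It states none for category B. The only place that does not count these pairs is a sample-size sentence, and the same section qualifies it.

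Original-diagnosis tissue is not a real ambiguity. The waiver in 5.2.3 covers patients with no biopsy at progression, so they have no tissue sample inside the interval that 5.1.4 and the design in section 4 require of a pair.

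**3. Size if category B pairs were left out.** The progressing share of the 55 is not given; 8.7 says only that most paired patients will be newly diagnosed. Assumed shares, with observed PPA near 80%:

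| Assumed share | n | Observed | 95% interval |
|---|---|---|---|
| 5% | 3 | 2/3 | 0.09–0.99 |
| 10% | 6 | 5/6 | 0.36–1.00 |
| 20% | 11 | 9/11 | 0.48–0.98 |
| 30% | 17 | 14/17 | 0.57–0.96 |
| All EGFR-positive pairs | 55 | 44/55 | 0.67–0.90 |

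Reaching 20 patients, the smallest column of Table 5, needs 20/55.2 = 36% progressing. A newly diagnosed majority does not rule that out.

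**4. Size with category B pairs in, as 8.2 and Table 4A read.** The share of the 40 with an in-window EGFR-positive biopsy is also assumed. With the 10% category A share (n = 6):

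| Assumed category B share | Pairs added | Stratum n | 95% interval near 80% |
|---|---|---|---|
| 10% | 4 | 10 | 0.44–0.98 (8/10) |
| 25% | 10 | 16 | 0.54–0.96 (13/16) |
| 50% | 20 | 26 | 0.61–0.93 (21/26) |

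Adding 10 or 20 pairs makes category B 10/65.2 = 15% or 20/75.2 = 27% of Table 4A. Across all the assumed shares the stratum runs from 3 + 4 = 7 to 17 + 20 = 37. Section 8.7 remarks that metastatic lesions are seldom biopsied, which argues for the lower category B shares.

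**The case for a change.** The best case for a change is that this study is sized on precision, so a promised stratum with no expected number has no planned precision. The label in 8.7 also disagrees with the synopsis, section 4, 5.1.3 and Table 6, which all leave tissue optional. If category B could be up to 27% of the primary denominator, the plan ought to say outright whether it is in. The cost would be a few sentences and no new samples.

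Two parts of this stand. The first mention in 8.7 is looser than the rest of the protocol, and no expected count of EGFR-positive progressing pairs is given.

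The rest does not carry. The analysis text already answers whether these pairs are in, so an analyst following 8.2 and Table 4A would include them. The progressing part of category A is not shown to be nearly empty either. Table 6 lists EGFR alterations as a subgroup within it, section 4 admits progression on any line, and category A turns away patients now progressing on the three drugs, not those who took one earlier. The study is descriptive with no hypothesis test, and 6.2.4 is one of six secondary objectives, covering every detected alteration. The suggested remedies also point in opposite directions: count the pairs, or narrow the objectives. That asks for a policy to be written down; it does not correct a wrong result. Because 6.2.4 already separates newly diagnosed from progressing patients, a reader can see whether the pooled PPA hides a difference.

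**Conclusion.** The concern does not hold as a defect. The plasma-only wording in 8.7 is sizing shorthand and excludes nobody. Sections 8.2 and 8.3 admit category B patients who have usable tissue, and the eight-week and no-new-therapy rules already govern those biopsies. What is left is a clerical looseness, plus an unstated subgroup size that analysts can fill sensibly from the existing rules and that 8.1 leaves to the Statistical Analysis Plan, to be finalized before the interim data lock.

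The stratum may be small: about 3 to 17 evaluable EGFR-positive pairs from category A, or about 7 to 37 with category B. Both ranges rest wholly on assumed shares (5% to 30% of 55, and 10% to 50% of 40). Exact intervals will report that imprecision honestly. The categories are taken from Tables 3 and 6, since Figure 1 is not available. No change to the plan follows.
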